7.7.2. Instructions for Reporting Special Situations

7.7.2.1. Instructions for Reporting Pregnancies

The investigator should report pregnancies in female study subjects that are identified after initiation of study medication and throughout the study, including the post study drug follow-up period, to Gilead PVE using the pregnancy report form within 24 hours of becoming aware of the pregnancy.

Refer to Section 7.3 and the eCRF completion guidelines for full instructions on the mechanism of pregnancy reporting.

The pregnancy itself is not considered an AE nor is an induced elective abortion to terminate a pregnancy without medical reasons.

Any premature termination of pregnancy (e.g. a spontaneous abortion, an induced therapeutic abortion due to complications or other medical reasons) must be reported within 24 hours as an SAE. The underlying medical reason for this procedure should be recorded as the AE term.

A spontaneous abortion is always considered to be an SAE and will be reported as described in Sections 7.1.1 and 7.1.2. Furthermore, any SAE occurring as an adverse pregnancy outcome post study must be reported to Gilead PVE.

The subject should receive appropriate monitoring and care until the conclusion of the pregnancy. The outcome should be reported to Gilead PVE using the pregnancy outcome report form. If the end of the pregnancy occurs after the study has been completed, the outcome should be reported directly to Gilead PVE. Gilead PVE contact information is as follows:

Email: PPD and Fax: PPD .

Pregnancies of female partners of male study subjects exposed to Gilead or other study drugs must also be reported and relevant information should be submitted to Gilead PVE using the pregnancy and pregnancy outcome forms within 24 hours. Monitoring of the subject should continue until the conclusion of the pregnancy. If the end of the pregnancy occurs after the study has been completed, the outcome should be reported directly to Gilead PVE, fax number PPD or email PPD

Refer to [Appendix 3](#) or Pregnancy Precautions, Definition for Female of Childbearing Potential, and Contraceptive Requirements.

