Filgotinib is contraindicated in pregnancy as there is a possibility of human teratogenicity / fetotoxicity in early pregnancy based on non-clinical data. Data from a drug-drug interaction study of filgotinib and hormonal contraceptives demonstrated that filgotinib does not alter the pharmacokinetics of representative hormonal contraceptives levonorgestrel / ethinyl estradiol. For male subjects, male condom should be used; for their female partners of childbearing potential, an accepted contraceptive method should also be considered. Details are outlined below.

Please refer to the latest version of the filgotinib investigator's brochure for additional information.

b. Contraception for Female Subjects of Childbearing Potential

The inclusion of female subjects of childbearing potential requires the use of highly effective contraceptive measures. Women must have a negative serum pregnancy test at Screening and a negative urine pregnancy test on the Day 1 Visit prior to randomization. Pregnancy tests will be performed at monthly intervals thereafter. In the event of a delayed menstrual period (>one month between menstruations), a pregnancy test must be performed to rule out pregnancy. This is true even for women of childbearing potential with infrequent or irregular periods. Female subjects of childbearing potential must agree to use one of the contraceptive methods below from Screening until either 35 days following the last dose of oral study drug or the contraception duration specified in the local adalimumab (HUMIRA®) label following the last dose of injected study drug (whichever is later).

- Complete abstinence from intercourse of reproductive potential (e.g. heterosexual intercourse). Abstinence is an acceptable method of contraception only when it is in line with the subject's preferred and usual lifestyle.

Or

- Consistent and correct use of 1 of the following methods of birth control listed below (as approved and available per local standards):
 - Intrauterine device (IUD) with a failure rate of <1% per year
 - Tubal sterilization
 - Essure micro-insert system (provided confirmation of success 3 months after procedure) (Not approved in Japan)
 - Vasectomy in the male partner (provided that the partner is the sole sexual partner and had confirmation of surgical success at least 3 months after procedure, with documentation of sperm-free ejaculate)

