These above described methods are considered *preferred methods* of highly effective contraception in this protocol.

Female subjects who wish to use a hormonally based method must agree to use it in conjunction with a barrier method (used either by the female subject or by her male partner). Female subjects who utilize a hormonal contraceptive as one of their birth control methods must have consistently used the same method for at least three months prior to study dosing.

Hormonally-based contraceptives and barrier methods permitted for use in this protocol are as follows:

- Hormonal methods (subject must agree to use with a barrier method, preferably, with a male condom)
 - Oral contraceptives (either combined estrogen / progestin or progesterone only)
 - Injectable progesterone (Not approved in Japan)
 - Subdermal Implants of levonorgestrel (Not approved in Japan)
 - Transdermal contraceptive patch (Not approved in Japan)
 - Contraceptive vaginal ring
- Barrier methods (subject must agree to use with a hormonal method)
 - Male or female condom (with or without spermicide)
 - Diaphragm with spermicide (Not approved in Japan)
 - Cervical cap with spermicide (Not approved in Japan)
 - Sponge with spermicide (Not approved in Japan)

All female subjects must also agree to refrain from egg donation and in vitro fertilization during study participation and until either 35 days following the last dose of oral study drug or the contraception duration specified in the local adalimumab (HUMIRA®) label following the last dose of injected study drug (whichever is later).

3) Contraception Requirements for Male Subjects

It is theoretically possible that a relevant systemic concentration may be achieved in a female partner from exposure to the male subject's seminal fluid. Therefore, male subjects with female partners of childbearing potential must agree to use condoms during study participation and for 90 days after the last study drug dose. Female partners of male study subjects should consider using one of the above methods of contraception as well. Male subjects must also agree to refrain from sperm donation during treatment and until at least 90 days after the end of dosing.

4) Unacceptable Birth Control Methods

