Birth control methods that are unacceptable include periodic abstinence (e.g. calendar, ovulation, symptothermal, post-ovulation methods), withdrawal (coitus interruptus), spermicides only, and lactational amenorrhea method (LAM). Female condom and male condom should not be used together.

5) Procedures to be Followed in the Event of Pregnancy

[figure not shown]
Subjects will be instructed to notify the investigator if they become pregnant at any time during the study, or if they become pregnant within 35 days of last study drug dose. Subjects who become pregnant or who suspect that they are pregnant during the study must report the information to the investigator and discontinue all the study drugs immediately. These subjects will be asked to continue in the study without taking study drug through the completion of the main study. Male subjects whose partner has become pregnant or suspects she is pregnant during the study or up to 90 days after the last dose of study drug are to report the information to the investigator.

Instructions for reporting pregnancy, partner pregnancy, and pregnancy outcome are outlined in Section 7.7.2.1.

6) Pregnancy Testing

All females of childbearing potential will have urine pregnancy testing every 4 weeks during the dosing period through the Safety Follow-up Visit (28-35 days after their last dose of study drug). During the periods where study visits are every 6-8 weeks, women should continue to have pregnancy tests every 4 weeks, using home pregnancy urine tests that will be provided to them. The site will call the subject every 4 weeks to obtain results of these pregnancy tests and will record the information in the source documents and eCRF. If a positive urine pregnancy test is reported, the subject will be asked to return to the clinic for a confirmatory serum pregnancy test.

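### For women who leave the study early, required contraception can outlast the instruction to report a pregnancy, because only the contraception rule carries an adalimumab label duration

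*Protocol*

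**What the plan says.** Protocol Appendix 3 sets the female contraception period in item 2b. It starts at Screening, and its end is worded as "until either 35 days following the last dose of oral study drug or the contraception duration specified in the local adalimumab"; after the brand name, the sentence closes with "label following the last dose of injected study drug (whichever is later"). The egg donation and in vitro fertilization rule repeats the period: "All female subjects must also agree to refrain from egg donation and in vitro fertilization during study participation and until either 35 days", and then gives the same adalimumab limb.

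Item 5 gives subjects the duty of telling the site about a pregnancy. That duty applies "if they become pregnant at any time during the study, or if they become pregnant within 35 days of last study drug dose". It mentions no label duration. Item 6 schedules pregnancy testing "during the dosing period through the Safety Follow-up Visit (28-35 days after their last dose of study drug").

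On the site's side, Section 7.7.2.1 has the investigator report pregnancies identified after study drug starts and "throughout the study, including the post study drug follow-up period". That period is neither defined nor linked to the label duration.

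Section 6.5 places the Safety Follow-up about 4 weeks after the last in-clinic visit. For Europe only, it adds calls 8, 12 and 16 weeks after the last injection, unless the last study visit is already 16 weeks or more after it.

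For male subjects, Appendix 3 uses 90 days after the last dose both for condom use and for reporting a partner's pregnancy.

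**The concern.** One appendix uses two end dates for the same risk. The contraception rule allows for a drug whose label may ask for more than 35 days. The notification rule repeats only the oral-drug figure. The two male periods agree, and the protocol gives no reason why the two female periods should not, so an oversight is more likely than a decision.

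At stake is the capture of pregnancies. A woman who has left the study may still be required to use contraception because of her last injection, become pregnant, and have no instruction to tell anyone. Every arm receives adalimumab or matching placebo injections under blind, so the longer contraception period applies to women in all four arms. No efficacy estimate depends on this. In the SAP it touches only the listing of subjects who become pregnant during the study (Section 7.5).

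**Working it through.** The documents state no figure to reproduce; the check is date arithmetic on the protocol's own rules.

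**Inputs**
- Oral limb: 35 days after the last oral dose (Appendix 3, item 2b).
- Injection limb: L days after the last injection, where L is the local label duration. L is not in the documents, so it is an assumption, ranged here from 35 to 180 days. The value of 112 days (16 weeks) is used as a reference because it is the longest post-injection follow-up in the documents (Section 6.5, Europe). It is not a label figure.
- Notification: during the study, or within 35 days of the last study drug dose (item 5).
- Last injection at about Week 14, day 98 counted from Day 1 (Section 3.2).
- Main Study end at Week 16, day 112; completion at Week 120, day 840 (Section 6.4).

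**Formulae.** Let O be the day of the last oral dose and I the day of the last injection.
- Contraception ends at max(O + 35, I + L).
- After leaving the study, notification ends at max(O, I) + 35.
- Gap = the first minus the second.

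**Case A, both drugs stop the same day (O = I).** For L of at least 35, the gap is L − 35. At L = 112: 112 − 35 = 77 days.

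**Case B, last injection Week 14 and last oral dose Week 16.** Contraception ends at max(147, 98 + L) and notification at 112 + 35 = 147. For L of at least 49, the gap is L − 49. At L = 112: 210 − 147 = 63 days.

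**Case C, oral drug continued in the LTE.** The gap is zero once O + 35 is at least 98 + L, that is, O of at least L + 63. At L = 112: O = 175 days, or Week 25.

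| Assumed L (days) | Gap, case A | Gap, case B | Case C: gap closes when last oral dose is at or after Week |
|---|---|---|---|
| 35 | 0 | 0 | 14 |
| 56 | 21 | 7 | 17 |
| 84 | 49 | 35 | 21 |
| 112 | 77 | 63 | 25 |
| 150 | 115 | 101 | 30.4 |
| 180 | 145 | 131 | 34.7 |

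**Week 120 completers.** A gap needs L above 840 + 35 − 98 = 777 days (111 weeks), so in practice there is none.

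**Stopping drug but staying on study.** If both drugs stop at Week 4 (day 28) and L = 112, contraception ends on day 140 (Week 20). A subject who stays to Week 16 and has the Safety Follow-up about 4 weeks later is in contact until about then, so little or no gap remains.

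**Europe.** With the last injection on day 98, the last extra call falls on day 98 + 112 = 210. That is the day on which contraception ends if L = 112.

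**Context.** SAP Section 1.3 reports that 13 of 67 subjects entered the LTE and that 7 of the 13 were terminated immediately. So 67 − 13 = 54 (81%) never entered, and 54 + 7 = 61 (91%) never entered or stopped at once. The number of women of childbearing potential is not given.

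**The case against.** The case on the other side has several parts, and much of it stands as a limit on scope.

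- **Notification is not confined to 35 days.** A reader might infer that only pregnancies within 35 days of the last dose are to be reported. Item 5 also covers any time during the study, and subjects who stop drug are meant to stay through Week 16. This confines the gap to women who have left.
- **Europe is largely covered.** The extra calls are protocol contacts reaching 16 weeks after the last injection, and the footnote describing them is attached to a schedule column that marks a pregnancy test. No text says pregnancy status is asked at each call, so they cover the gap largely, not demonstrably. SAP Section 3.3 also lists Australia, Canada, New Zealand, the United States and Japan, where these calls do not apply.
- **L is unseen.** A gap at any particular site cannot be shown from the documents. This stands, although the later-of-two-dates wording itself provides for a label period that outlasts the oral limb.
- **Most subjects receive placebo injections.** Under 2:2:1:2 allocation, 6 of 7 subjects are assigned placebo injections. A reader might infer that adalimumab exposure is under-reported across all injected subjects, but those 6 have none to miss. Under blind, however, the contraception rule applies to them equally.
- **There are backstops.** Section 7.7.2.1 requires reporting of serious adverse pregnancy outcomes after the study, and Section 7.3 covers later SAEs judged relevant to study drug. Both help only if the site learns of the event.
- **The two periods need not coincide.** No passage says they must. But none explains the difference either, and the male periods do match.

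**Conclusion.** The mismatch is real but minor, and it belongs to a limited group: women of childbearing potential who leave in the Main Study or early in the LTE, mainly outside Europe, where the local label duration exceeds 35 days.

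The size depends on the assumed L. At 112 days it is 77 days if both drugs stop together and 63 days on the Week 14 and Week 16 schedule. It is zero at 35 days or less, and zero at 112 days once oral dosing reaches about Week 25.

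Two stronger conclusions are tempting. One is that pregnancies did go unreported: the documents show only that no instruction covers the period, and a subject may still volunteer the information. The other is that the 54 subjects who never entered the LTE are the number at risk: that count includes men, women not of childbearing potential and every region and arm, so it is context only.

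**What to change.** Reconcile Appendix 3 items 2b, 5 and 6, the egg donation and in vitro fertilization rule, and Sections 7.7.2.1 and 6.5, so that the contraception and pregnancy notification periods are consistent with each other. State in Section 7.7.2.1 what the follow-up period after study drug means. Which duration applies is for the sponsor to decide; this review takes no position on it.

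As a check, if notification followed the same later-of-two-dates rule as contraception, the unmatched period would be 0 days for any L.

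The cost is a few lines of protocol text and a line in the subject instructions. If the notification period becomes longer, the added burden is a slightly longer passive reporting period, with no added visits. The study has already been terminated, so the value now lies in reading its pregnancy listing and in any reuse of this text.

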Appendix 4. Management of Clinical and Laboratory Adverse Events

For study specific interruption and stopping criteria, please refer to Section 3.5.

Appendix 5. Laboratory Assessment Table

Hematology	Chemistry	Urinalysis	Other
Hematocrit Hemoglobin Platelet count Red blood cell (RBC) count Red blood cell indices: RBC Morphology and MCV MCH MCHC White blood cell (WBC) count Differentials (absolute and percentage), including: Lymphocytes Monocytes Neutrophils Eosinophils Basophils	Alkaline phosphatase Aspartate aminotransferase (AST) Alanine aminotransferase (ALT) Gamma-glutamyl transpeptidase (GGT) Total bilirubin Direct and indirect bilirubin Total protein Albumin Bicarbonate Blood urea nitrogen (BUN) Calcium Chloride Serum creatinine* Glucose Phosphorus Magnesium	Appearance Blood Color Glucose Specific gravity Nitrites Leukocyte esterase pH Protein Urobilinogen Reflex to microscopic urinalysis if dipstick result is abnormal.	Urine drug screen Leukocyte subsets (TBNK blinded to subjects and investigators) vfpBMC** C-reactive protein (hsCRP) (blinded to subjects and investigators for all visits, blinded to Sponsor for all Main Study visits except Day 1 Visit) CCI QuantiFERON®- TB GOLD Plus††
Endocrine at screening only	Potassium Sodium Amylase Lipase	Serology	Pregnancy
Hemoglobin A1c TSH FSH (for women only)†††	Lipid profile (fasting): Triglycerides Cholesterol and its subfractions (high-density lipoprotein [HDL] and low-density lipoprotein [LDL])	Hepatitis BsAg and core Ab (if positive core Ab, then reflex Hep B DNA) Hepatitis C Ab (if positive, then reflex HCV RNA) HIV	In females of childbearing potential: Serum β-hCG (Screening and if positive urine β-hCG) Urine β-hCG (all other visits)†

* Creatinine clearance is calculated by the Cockcroft-Gault equation {Cockcroft 1976} using actual body weight (BW).

$$\text{Male: } CL_{cr} \text{ (mL / min)} = \frac{[140 - \text{age (years)}] \times \text{BW(kg)}}{72 \times [\text{Serum Creatinine (in } \frac{\text{mg}}{\text{dL}})]}$$

$$\text{Female: } CL_{cr} \text{ (mL / min)} = \frac{[140 - \text{age (years)}] \times \text{BW(kg)} \times 0.85}{72 \times [\text{Serum Creatinine (in } \frac{\text{mg}}{\text{dL}})]}$$

** vfpBMCs collected in North America only.

† During the periods where study visits are every 6-8 weeks, women should continue to have pregnancy tests every 4 weeks, using home pregnancy urine tests that will be provided to them. The site will call the subject every 4 weeks to obtain results of these pregnancy tests and will record the information in the source documents and eCRF.

†† In the event QuantiFERON®-TB GOLD Plus is not available, an equivalent TB test may be substituted by the central lab.

††† Investigator and the Sponsor may re-evaluate a subject's childbearing potential during the study (including the use of FSH values if appropriate).

Appendix 6. Primary and Key Secondary Null Hypotheses

The primary null hypotheses to be tested are:

- H1: Filgotinib 200 mg is not different to placebo based on the response rate of ACR20 at Week 12
- H2: Filgotinib 100 mg is not different to placebo based on the response rate of ACR20 at Week 12

[figure not shown]
Hypotheses on the key secondary endpoints will only be tested if the primary hypothesis H1 or H2 on that dosing regimen is rejected. The following list is the full list of all the null hypotheses on the key secondary endpoints to be tested. The order of the key secondary null hypotheses to be tested will be specified in the SAP and is not reflected below.

- H3: Filgotinib 200 mg is not different to placebo based on the response rate of ACR50 at Week 12
- H4: Filgotinib 100 mg is not different to placebo based on the response rate of ACR50 at Week 12
- H5: Filgotinib 200 mg is not different to placebo based on the change from Baseline in HAQ-DI at Week 12
- H6: Filgotinib 100 mg is not different to placebo based on the change from Baseline in HAQ-DI at Week 12
- H7: Filgotinib 200 mg is not different to placebo based on the change from Baseline in SF-36v2 PCS at Week 16
- H8: Filgotinib 100 mg is not different to placebo based on the change from Baseline in SF-36v2 PCS at Week 16
- H9: Filgotinib 200 mg is not different to placebo based on the change from Baseline in LEI at Week 16, in subjects with enthesitis at Baseline
- H10: Filgotinib 100 mg is not different to placebo based on the change from Baseline in LEI at Week 16, in subjects with enthesitis at Baseline
- H11: Filgotinib 200 mg is not different to placebo based on the response rate of PASI75 at Week 16, in subjects with psoriasis covering $\geq 3\%$ of the BSA at Baseline
- H12: Filgotinib 100 mg is not different to placebo based on the response rate of PASI75 at Week 16, in subjects with psoriasis covering $\geq 3\%$ of the BSA at Baseline
- H13: Filgotinib 200 mg is not different to placebo based on the response rate of MDA at Week 16

- H14: Filgotinib 100 mg is not different to placebo based on the response rate of MDA at Week 16
- H15: Filgotinib 200 mg preserves no more than 50% of the effect of adalimumab (as compared to placebo) on the response rate of ACR20 at Week 12
- H16: Filgotinib 100 mg preserves no more than 50% of the effect of adalimumab (as compared to placebo) on the response rate of ACR20 at Week 12
- H17: Filgotinib 200 mg is not different to placebo based on the change from Baseline in FACIT-Fatigue at Week 16
- H18: Filgotinib 100 mg is not different to placebo based on the change from Baseline in FACIT-Fatigue at Week 16
- H19: Filgotinib 200 mg is not different to placebo based on the change from Baseline in LDI at Week 16, in subjects with dactylitis at Baseline
- H20: Filgotinib 100 mg is not different to placebo based on the change from Baseline in LDI at Week 16, in subjects with dactylitis at Baseline

Appendix 7. Hypothesis Testing Strategy

Note: Below figure is for illustration purpose and does not reflect the order of key secondary hypotheses.

Appendix 8. Protocol, Day Numbering

Protocol Day Numbering			# Calendar Days after Day 1	Example Visit Date
Start of 1st Week	Monday	Day 1	-	16-Sep-19
	Tuesday	Day 2	1	17-Sep-19
	Wednesday	Day 3	2	18-Sep-19
	Thursday	Day 4	3	19-Sep-19
	Friday	Day 5	4	20-Sep-19
	Saturday	Day 6	5	21-Sep-19
	Sunday	Day 7	6	22-Sep-19
Start of 2nd Week	Monday	Day 8	7	23-Sep-19
	Tuesday	Day 9	8	24-Sep-19
	Wednesday	Day 10	9	25-Sep-19
	Thursday	Day 11	10	26-Sep-19
	Friday	Day 12	11	27-Sep-19
	Saturday	Day 13	12	28-Sep-19
	Sunday	Day 14	13	29-Sep-19
Start of 3rd Week	Monday	Day 15	14	30-Sep-19
	Tuesday	Day 16	15	1-Oct-19
	Wednesday	Day 17	16	2-Oct-19
	Thursday	Day 18	17	3-Oct-19
	Friday	Day 19	18	4-Oct-19
	Saturday	Day 20	19	5-Oct-19
	Sunday	Day 21	20	6-Oct-19

NOTE: Vendors may have different *Day Numbering* (i.e. start with Day 0); however, the # *Calendar Days after Day 1* will remain consistent.

